3.1 Study design

Patients will be allocated to 3 main treatment arms:

- Arm A (patients with new-onset plaque psoriasis to be treated with secukinumab): composed of Arm A1 (A1a and A1b) and Arm A2
- Arm B1 (patients with new-onset plaque psoriasis to be treated with nb-UVB): composed of Arm B1a and Arm B1b
- Arm C (patients with chronic plaque psoriasis to be treated with secukinumab): composed of Arm C1 and Arm C2

An overview of the treatment arms is summarized in [Table 3-1](#).

Table 3-1 Summary information for study arms

Arm	Psoriasis duration	Study part	Treatment	Treatment duration
A1a	new-onset	Main	Secukinumab	52 weeks
A1b	new-onset	Main and mechanistic	Secukinumab	52 weeks
A2	new-onset	Mechanistic	Secukinumab	104 weeks
B1a	new-onset	Main	nb-UVB	52 weeks
B1b	new-onset	Main and mechanistic	nb-UVB	52 weeks
C1	chronic	Mechanistic	Secukinumab	52 weeks
C2	chronic	Mechanistic	Secukinumab	104 weeks

The design consists of a Main Study and a Mechanistic Sub-study.

The Main Study will be multicenter, randomized, 2-treatment-arm (secukinumab and nb-UVB), parallel-group and open-label. It will include 3 clinical epochs (Screening Epoch, Treatment Epoch, and Follow-up Epoch) involving all patients in Arms A1 (A1a and A1b) and B1 (B1a and B1b).

The Mechanistic Sub-study will be open-label and comprise 5 treatment arms (A1b, A2, B1b, C1, and C2). It will include 2 epochs (Screening Epoch and Treatment Epoch) for patients in Arms C1 and C2. Patients from Arms A1b, A2, and B1b will undergo the 3 clinical epochs of the Main Study.

Details of the Main Study and the Mechanistic Sub-study with the number of patients and treatment regimen for each arm are provided in the following sub-sections. The randomization to the treatment arms is outlined in [Section 5.3](#).

Screening Epoch

Patient's eligibility for the study will be assessed at the screening visit (Day -28 to Day -1 before baseline) and at the baseline visit (see [Table 6-1](#)).

Main Study

Treatment Epoch

At the baseline visit, eligible patients will be randomized to one of the following treatment arms (see [Figure 3-1](#)):

- **Arm A1:** patients with new-onset plaque psoriasis will receive 300-mg secukinumab by s.c. injection at baseline, Weeks 1, 2, 3, 4 and then every 4 weeks until Week 48 inclusive

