- **Arm B1:** Subjects with new-onset plaque psoriasis will receive either 1 or 2 cycles of nb-UVB of 12 weeks each with a maximum break of 28 weeks between cycles (subjects with PASI 90 at Week 40 will not receive a second treatment cycle). Only during the first 4 weeks of each cycle, nb-UVB treatment will be given in combination with topical calcipotriol 50 µg/g and betamethasone 0.5 mg/g.

Follow-up Phase

At the end of the Treatment Phase at Week 52, all subjects with \geq PASI 50 response from Arm A1 and Arm B1 will enter the Follow-up Phase. Subjects who do not achieve a PASI 50 response, will have all assessments of end of study (EOS) and be discontinued from the study.

[figure not shown]
During the Follow-up Phase, subjects will not receive study treatment; they will be observed maximally until Week 208, and compared regarding the proportion of them who achieve PASI 90 response at Week 104.

Subjects who relapse (those who experience a loss of 50% of the maximum improvement in PASI score achieved during the Treatment Phase) will have all assessments of EOS and be discontinued from the study.

If no relapse occurs, subjects who achieve $<$ PASI 90 at Week 52 in Arms A1 (A1a and A1b) and B1 (B1a and B1b) will be followed until Week 104, while subjects who achieve \geq PASI 90 at Week 52 will be followed until Week 208.

The investigator should provide ongoing adequate care for subjects who relapse. If the investigator decides to continue treating the subjects with secukinumab, a new loading dose of commercially available secukinumab could be considered. The treatment with secukinumab after relapse will be out of scope of the study.

Figure 1-1 Study design – Main study

BL = baseline, EOS = end of study, KSE = key secondary endpoint, nb-UVB=narrow-band ultraviolet B, PASI = psoriasis area and severity index, PE = primary endpoint, R = randomization.

Mechanistic Sub-study

A separate informed consent will be obtained from study subjects who agree on having skin biopsies taken and therefore become eligible for this Mechanistic Sub-study. Besides the biopsies, subjects will undergo the same assessments as in the Main Study.

Treatment Phase

At the Baseline Visit, eligible subjects will be allocated to one of the treatment arms of the mechanistic Sub-study (see [Figure 1-1](#)):

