Subjects who complete treatment phase at Week 52 (for Arm A1 and Arm B1) and Week 104 (for Arm A2) but discontinue before entering follow up phase (despite PASI 50/PASI 90 requirement met) will be assumed as treatment phase completers. The Investigator or Staff will fill additional follow-up disposition eCRF with the reason for discontinuation from the study. In this manner, all the reasons for subjects discontinuation from the study will be captured.

In the Main study for final analysis, subject disposition status with reasons for discontinuation as per CRF will be calculated for duration of Baseline – Week 52. Whereas , for follow-up epoch the duration is Week 52 – Week 104 , Week 104 – Week 152 and Week 152 – Week 208 and for entire follow-up epoch duration Week 52- Week 208. An analysis will be performed for Randomized set and follow-up efficacy analysis set.

For the follow-up epoch, an analysis will be repeated from subgroup of subjects who entered follow-up phase , percentage calculations based on the subject entered follow-up phase. Subject disposition in the follow-up phase for the above mentioned duration (Week 52 – Week 104, Week 104 – Week 152, Week 152 – Week 208) is also performed with respect to the PASI categories (PASI 50-89, PASI 75, PASI 90 and PASI 100) at Week 52. An analysis will be performed for mFAS.

For the mechanistic sub-study, subjects disposition over Screening, treatment and follow-up phase are summarized similarly in separate tables at time of Week 52 interim analysis. However, at time of final analysis and if required at time of Week 104 interim analysis treatment arms are presented separately as per [section 2.1](#). For W104 IA and Final analysis subject disposition status with reasons for discontinuation will be calculated for duration of Baseline – Week 52 , Baseline – Week 104 and Week 52 – W104 for Treatment epoch (Arm A2: Week 104) . Whereas , for follow-up epoch the duration is Week 52 – Week 104 (Arm A1 and B1) , Week 104 – Week 152 , Week 152 – Week 208 and Week 52 – Week 208. For the follow-up epoch, an analysis will be repeated for the subgroup of subjects who entered follow-up phase , percentage calculations based on all the subject entered follow-up phase.

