Scatter plot will be produced for study day analysis for Week 52 time window (Day 310 to 421) and PASI score stratified by pre pandemic and during pandemic phase. In Y axis PASI score and in X axis study day will be plotted.

For the figures with pre-pandemic and during pandemic phase, the definition is:

If the treatment period end date was before pandemic start, the pandemic phase is defined as “pre-pandemic”, otherwise defined as “during pandemic”. If a subject discontinued from treatment in treatment period and the discontinued date from study was before pandemic start, then the pandemic phase defined as “pre-pandemic”, otherwise defined as “during pandemic”. Pandemic start is defined as – 01MAR2020

Observed PASI score at Week 52 will be listed by pandemic phase (pre- and during-pandemic).

Descriptive analysis of absolute value of PASI scores (observed data) at Weeks 16, 24, 36, 52 up to Week 208 for all treatment arms will be provided. Descriptive analysis of absolute value of PASI score with MI method will be performed up to Week 104 only, where the missing PASI score will be imputed using multiple imputation. Graphical representation will be done using Dot plot and time course plot for PASI 90 response at week 52 and PASI score over time respectively. Percent change from baseline PASI score (multiple imputation) over time will be presented graphically for individual subjects through Spaghetti plots.

Follow-up phase visits where number of subjects in treatment group are very low it may give large imputed values and the covariance matrix in MCMC process can not be computed, hence, the analysis tables and graphs will be presented up to Week 104. Additionally, same analysis tables and graphs will be also repeated LOCF (for continuous endpoints) or NRI (for binary endpoints) . upto Week 104 Data beyond week 104 and upto Week 208 will only be summarized as observed data. All analysis will be performed using mFAS set.

A Separate Time course plot will be generated to display the Percentage (%) of patients with Total PASI absolute score < 3 with (NRI) approach upto Week 104.

For Mechanistic sub-study the summary statistics for PASI absolute score and change from baseline to post-baseline visits is summarized for FAS. Time course plot for percentage change from baseline PASI score and absolute PASI score will be provided for each treatment group separately. At time of Final analysis PASI score will be listed for FAS set.

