2.6.3 Handling of missing values/censoring/discontinuations

As specified in [Section 2.5.3](#), the method of handling missing responses for the key secondary variable will also be the modified multiple imputation method, similarly as for the primary endpoint analysis. Subjects who relapse (a loss of 50% of the maximum improvement in PASI score) or who do not achieve a PASI 50 response at Week 52, will be considered non-responders in addition to those who discontinue the study before Week 104 because of lack of efficacy or AEs.

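### LOCF for continuous PASI runs to Week 104, so end-of-treatment and relapse-visit values appear as treatment-free PASI and can overstate mean improvement in follow-up

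*SAP*

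**What the plan says.** SAP section 2.5.4 plans three kinds of PASI display after Week 52. The first is multiple imputation (MI): "Descriptive analysis of absolute value of PASI score with MI method will be performed up to Week 104 only". The second is observed data, to Week 208. The third is added alongside: "same analysis tables and graphs will be also repeated LOCF (for continuous endpoints) or NRI (for binary endpoints", again up to Week 104. The population is the modified full analysis set: "All analysis will be performed using mFAS set". A patient who leaves early therefore stays in the denominator.

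The design fixes what can be carried forward:

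- SAP section 1.1: "During the Follow-up Phase, subjects will not receive study treatment". In Arm A1, dosing is weekly at first and "then every 4 weeks until Week 48 inclusive" (Protocol section 3.1). The Week 52 PASI is thus taken 4 weeks after the last dose.
- Patients below PASI 50 at Week 52, and patients who relapse (lose half of their maximum improvement), are withdrawn (SAP section 1.1).
- SAP section 2.3.1 foresees patients who "discontinue before entering follow up phase (despite PASI 50/PASI 90 requirement met".
- For the binary Week 104 endpoint, SAP section 2.6.3 sets a rule. Relapsers and patients below PASI 50 at Week 52 "will be considered non-responders in addition to those who discontinue the study before Week 104 because of lack of efficacy or AEs".

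The visible text has no matching rule for continuous PASI under LOCF. The instruction not to carry baseline values forward belongs to the LOCF analysis of PASI 90 at Week 52. Parts of SAP section 2.13 are blacked out and are not counted as missing.

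**The concern.** The trial asks whether disease stays away once treatment stops. In follow-up, PASI goes missing largely because of the outcome: a patient leaves on relapsing and is not measured again. From that visit LOCF holds the patient at the relapse value, whatever the disease does next. A responder who leaves at Week 52 is held at an end-of-treatment value through Weeks 64 to 104. Both values are then plotted at treatment-free visits. A mean curve built this way stops falling for each patient at exit, so it can suggest more residual benefit than there is. It may also be taken for the cautious check on MI, because section 2.5.4 introduces it right after warning that MI can misbehave at sparse follow-up visits.

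**Working it through.** **1. The plan's own Week 104 figure.** The documents give no expected mean PASI for follow-up. Their only Week 104 quantity is the key secondary power (Protocol section 9.9): about 89% for 21% v 4%, 80 per arm, Fisher's exact test, 1-sided 0.025. Exact enumeration gives 90.0%, so it reproduces. That endpoint uses modified MI with relapse as non-response, so LOCF does not enter it.

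**2. Bound for one patient.** Error = carried value − true untreated value at Week 104, in points of % PASI improvement.

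- Relapser: the carried value is at most half the maximum improvement. A maximum of 95% (assumed) gives at most 47.5%. If the truth lies between 0 and 47.5%, the error is 0 to +47.5. If PASI recovers to 67.5%, it is −20.
- Responder leaving at Week 52 with 95% (assumed): the error is 0 to +95. If 5 to 20% of an arm does this, the arm mean rises by at most 0.05 × 95 = 4.75 to 0.20 × 95 = 19 points.
- Exit below PASI 50: the carried value is below 50%, which already reads as failure.

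**3. With the planned exits.** Protocol section 9.9 assumes 7% (A1) and 16% (B1) leave before Week 104 for lack of efficacy, AEs or relapse. If all are relapsers held at 47.5% who truly return to baseline, the means rise by 0.07 × 47.5 = 3.3 and 0.16 × 47.5 = 7.6 points. The A1 − B1 difference moves by 3.3 − 7.6 = −4.3, against secukinumab.

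**4. Simulation with no disease modification.** All inputs here are assumptions. There are 200,000 patients per arm. Week 52 improvement is Beta(11, 1) in A1 and Beta(1.9, 0.75) in B1, giving PASI 90 of about 69% and 29%, close to the planned 70% and 28%. Improvement then decays exponentially with the same lognormal half-life distribution in both arms (log-SD 0.5). Patients leave at Week 52 if below 50%, or at the first of Weeks 64, 76, 88, 100 or 104 at which improvement is no more than half the Week 52 value. Mean % improvement at Week 104, no other exits:

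| Median half-life (weeks) | A1 true | A1 LOCF | A1 error | B1 true | B1 LOCF | B1 error |
|---|---|---|---|---|---|---|
| 10 | 5.0 | 31.3 | +26.3 | 4.0 | 28.8 | +24.8 |
| 20 | 17.5 | 37.3 | +19.8 | 13.7 | 33.0 | +19.3 |
| 30 | 28.5 | 41.0 | +12.5 | 22.3 | 35.7 | +13.4 |
| 60 | 49.0 | 51.8 | +2.8 | 38.3 | 43.3 | +5.0 |
| 120 | 66.2 | 66.3 | +0.1 | 51.7 | 53.7 | +2.0 |

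The A1 − B1 difference goes from 5.0 − 4.0 = 1.0 to 31.3 − 28.8 = 2.5 at 10 weeks (wider), and from 28.5 − 22.3 = 6.2 to 41.0 − 35.7 = 5.3 at 30 weeks (narrower).

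If 10% of patients at PASI 50 or better also leave at Week 52, LOCF in A1 gives 37.3, 42.7 and 46.1 at 10, 20 and 30 weeks. The errors become about 32, 25 and 18 points.

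**5. Alternatives in the same model, A1, no other exits.**

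- Regression imputation on earlier PASI within arm, with large samples, stays within about 3 points of the truth at every half-life. This is expected, because exit is triggered by an observed PASI. With 80 patients it is less secure: at 20 weeks about 4% remain observed at Week 104 (0.04 × 80 ≈ 3 patients), and at 30 weeks about 17% (≈ 14).
- Setting relapse and below-PASI-50 exits to baseline PASI gives about 7% at 30 weeks (error −21, against +12.5 for LOCF) and 36% at 60 weeks (−13 against +3).

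**The case against.** The strongest reply has four parts.

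First, this is a supplementary descriptive display beside MI and observed data, and no visible hypothesis test uses it. That stands, and it limits the weight of the point.

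Second, the LOCF curve does not hide loss of control. In the simulation the A1 mean falls from 92% at Week 52 to 41% (half-life 30 weeks) or 31% (10 weeks), a drop of 51 to 60 points. A relapser held at half of maximum improvement can never show as PASI 75 or PASI 90. This also stands. A reader might infer that the curve would look like a remission plateau, but the study's own relapse definition rules that out.

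Third, LOCF is less flattering than the observed-data summary: at 30 weeks the observed A1 mean is 51%, LOCF 41% and the truth 28%. That is correct, but the observed summary plainly describes only those who remain, whereas LOCF claims to describe everyone. Being lower than a selected mean does not make it unbiased.

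Fourth, the half-lives of 10 to 30 weeks are fast: 86 to 100% of A1 relapses by Week 104, and true PASI 90 is about 0%, against the planned 21% v 4%. This stands as a limit on size. With slow decay the error nearly vanishes in A1.

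**Conclusion.** The point holds in conditional form. As written, section 2.5.4 shows Week 52 and relapse-visit values as treatment-free PASI up to Week 104, and this can overstate mean improvement in follow-up. Under assumed exponential decay in A1 with no other exits, the overstatement at Week 104 is about 12 to 26 points for half-lives of 30 down to 10 weeks, about 3 at 60 and about 0 at 120. It is larger if responders leave at Week 52. The documents contain no follow-up means, so no single size can be given, and recovery after relapse could reverse the sign.

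Three stronger readings are not supported:

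- That lasting control is overstated whatever happens: the size, and even the sign, depend on the course after exit.
- That the bias favours secukinumab: the difference between arms moves either way, and under the planned exits it moves against secukinumab.
- That LOCF and non-responder imputation contradict each other: a relapser at 47% improvement is a PASI 90 non-responder on both.

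The primary and key secondary conclusions are untouched.

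**What to change.** In SAP section 2.5.4, limit LOCF tables and graphs of continuous PASI to the Treatment Epoch visits (Weeks 16 to 52). State that no Treatment Epoch or relapse-visit value is carried into Weeks 64 to 104. For those visits rely on the MI, non-responder and observed-data displays already planned, and print the number observed per arm at each visit so that readers can see where MI rests on few patients.

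Do not adopt baseline PASI for leavers as the default replacement. At half-lives of 30 to 60 weeks, without other exits, it is further from the truth than LOCF. At most it is a display labelled as a worst case.

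The cost is a wording change and minor programming, with no new data. One supportive display loses its follow-up part.

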- **Arm B1:** patients with new-onset plaque psoriasis will receive 1 or 2 cycles of nb-UVB of 12 weeks each with a maximum break of 28 weeks between cycles (patients with PASI 90 at Week 40 will not receive a second treatment cycle). Only during the first 4 weeks of each cycle, nb-UVB treatment may be given in combination with topical calcipotriol 50 µg/g and betamethasone 0.5 mg/g

Follow-up Epoch

At the end of the Treatment Epoch at Week 52, all patients with \geq PASI 50 response from Arm A1 and Arm B1 will enter the Follow-up Epoch. Patients who do not achieve a PASI 50 response, will have all assessments of EOS and be discontinued from the study.

During the Follow-up Epoch, patients will not receive study treatment; they will be observed maximally until Week 208, and compared regarding the proportion of them who achieve PASI 90 scores at Week 104.

[figure not shown]
Patients who relapse (those who experience a loss of 50% of the maximum improvement in PASI score achieved during the Treatment Epoch) will have all assessments of EOS and be discontinued from the study.

If no relapse occurs, patients who achieve $<$ PASI 90 at Week 52 in Arms A1 (A1a and A1b) and B1 (B1a and B1b) will be followed (according to the visit schedule outlined in [Table 6-3](#))

until Week 104, while patients who achieve \geq PASI 90 at Week 52 will be followed until Week 208.

The investigator should provide ongoing adequate care for patients who relapse. If the investigator decides to continue treating the patients with secukinumab, a new loading dose of commercially available secukinumab could be considered. The treatment with secukinumab after relapse will be out of scope of the study.

Figure 3-1 Study design – Main Study

BL = baseline, EOS = end of study, KSE = key secondary endpoint, nb-UVB=narrow-band ultraviolet B, PASI = psoriasis area and severity index, PE = primary endpoint, R = randomization.

Mechanistic Sub-study

A separate informed consent will be obtained from study patients who agree on having skin biopsies taken and therefore become eligible for this Mechanistic Sub-study. Besides the biopsies, patients will undergo the same assessments as in the Main Study.

Treatment Epoch

At the baseline visit, eligible patients will be allocated to one of the treatment arms of the Mechanistic Sub-study (see [Figure 3-1](#) and [Section 5.3](#)):

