2.1 Data analysis general information

Data will be analyzed using the Statistical Analysis Software (SAS) Version 9.4 or higher, according to the data analysis section (Section 9) of the protocol. This information will also be available in Appendix 16.1.1 of the Clinical Study Report (CSR). Additional important information as appropriate will be given in listings and the CSR. Final study CSR document will include the reports of Main study, mechanistic study and additional analysis.

Unless otherwise specified, the statistical hypothesis tests will be conducted against 1-sided alternative hypothesis, employing a 2.5% level of significance. For other analyses, p-values will be presented as 2-sided, employing a 5% level of significance. Two-sided 95% confidence intervals will be displayed.

Efficacy, safety, and other data will be summarized descriptively as follows:

- for continuous variables, descriptive summary statistics (number of subjects (n), mean, standard deviation (SD), median, minimum, maximum and lower/upper quartiles) for absolute and change (absolute and relative) from Baseline values will be reported by treatment arms (of the Main Study and of the Mechanistic Sub-study, as applicable).
- for categorical variables, frequency (n) and percentage (%) will be presented by treatment arms (of the Main Study and of the Mechanistic Sub-study, as applicable). Percentages will be calculated with respect to the number of evaluable subjects (m) out of the total number of subjects in the analysis set (N) of interest.

For Mechanistic Sub-study at time of final analysis or Week 104 interim analysis (if required) treatment arms are presented by duration of psoriasis for each treatment arm separately as;

New-onset : Arm A1b , Arm A2 and Arm B1b.

Chronic : Arm C1 and Arm C2

Total (wherever required).

In Main Study, after Week 104 subjects continued into the study are low, hence if statistical analysis where missing data is handled using Imputation method then analysis will be performed upto Week 104 unless mentioned otherwise. However, In Mechanistic Sub-study

due to limited number of subjects after Week 104 , listings will be only provided including disposition summary for the final analysis.

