2.7 Analysis of additional secondary objective(s)

2.7.1 IGA mod 2011 0 or 1 response

The secondary efficacy variable is the proportion of all randomized subjects who achieve at least IGA 0/1 response at Week 52. Subjects will be considered as **IGA mod 2011 0 or 1 responder** if they achieve a score of 0 or 1 and improve by at least 2 points on the IGA mod 2011 scale compared to Baseline.

IGA mod 2011 0 or 1 response at Week 52 will be analyzed using a logistic regression model similar to the primary analysis, with treatment as an explanatory variable and significant variables among Baseline IGA mod 2011 score, age, and BMI, and their interactions with treatment. Forward selection procedure based on the likelihood ratio test would be used to select the best subset of covariates. The estimated adjusted odds ratio for Arm A1 versus Arm B1 will be displayed along with the associated 95% confidence interval.

If there are issues related to the convergence of the logistic regression model, we will use a 1-sided Wald's test will be performed. This analysis will be based on the FAS and mFAS.

Time course plot for IGA mod 2011 0/1 response rates at scheduled visits upto Week 104 for imputed data and upto Week 208 based on observed data.

Handling of missing data

Missing IGA 0/1 response values will be imputed with non-response regardless of the reason for the missing data (e.g., premature study discontinuation, missed visit, or administrative issue).

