2.13.4 Investigators global assessment mod 2011 score and response over time

Treatment Arm A1 will be compared with Arm B1 based on IGA mod 2011 0/1 responses at Week 104 using a similar logistic regression model as described in [Section 2.7.1](#).

Further, IGA mod 2011 0/1 responses at Week 104 will be analyzed by means of logistic regression model similar to the secondary analysis with treatment as a predictor variable and the significant variables among Baseline IGA mod 2011 score, age, and body mass index, and their interactions with treatment. Forward selection procedure based on the likelihood ratio test would be used to select the best subset of covariates. The estimated adjusted odds ratio will be displayed along with the associated 95% confidence interval.

In case of low responses achieved, the logistic regression model may not converge OR in case of non-significant difference between treatment groups any covariate may not get selected in logistic regression model with either of selection method . In such cases, we will use Wald's 1-sided test for comparison of treatment groups in IGA 0/1 score at Week 104.

IGA mod 2011 score will be summarized descriptively, using number and percentages by visits. Confidence intervals for response rates will be derived as well based on the score method including continuity correction ([Newcombe 1998](#)).

For the treatment arms in the Mechanistic Sub-study, the above-stated analyses will also be repeated for both IGA score and IGA mod 2011 0/1 response over the 52 weeks of the Treatment Phase based on the observed data (i.e., until Week 52 for Arms A1b, B1b, and C1, and until

Week 104 for Arms A2 and C2) and Follow-up phase. Summary statistics for IGA mod 2011 0/1 response for treatment phase will also be performed with Non-responder imputation method upto Week 104. For follow-up phase analysis if required separate analysis is performed for change from Week 52 (For Arm A2; Week 104) to post-baseline visits in follow-up phase.

Handling of missing data

Missing IGA 0/1 response values will be imputed with non-response regardless of the reason for the missing data (e.g., premature study discontinuation, missed visit, or administrative issue).

Analysis will be based on the FAS and mFAS.

An analysis for imputed data (NRI approach) will be performed upto Week 104 and based on observed data will be performed upto Week 208.

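### After Week 104 the Main Study response summaries use observed patients only, although planned exits and relapse remove poorer responders, so the displayed rate can hold or rise while the share of patients still in response falls

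*SAP*

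**What the plan says.** **Data handling.** SAP 2.5.4 ends the imputed PASI tables and graphs at Week 104, together with their LOCF and NRI repeats, and then states: "Data beyond week 104 and upto Week 208 will only be summarized as observed data". SAP 2.7.1 plans a time-course plot of IGA 0/1 "response rates at scheduled visits upto Week 104 for imputed data and upto Week 208 based on observed data". SAP 2.13.4 repeats the split: "An analysis for imputed data (NRI approach) will be performed upto Week 104 and based on observed data will be performed upto Week 208". For categorical variables, SAP 2.1 says: "Percentages will be calculated with respect to the number of evaluable subjects (m"), out of the N in the analysis set.

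**Stated reasons for stopping.** SAP 2.1 and 2.5.4 cite the low number of subjects after Week 104. SAP 2.5.4 adds that the covariance matrix in the MCMC step may not be computable.

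**Who is still observed.** Under SAP 1.1 and Protocol 3.1, patients below PASI 50 at Week 52 leave then. Absent relapse, subjects below "PASI 90 at Week 52 in Arms A1 (A1a and A1b) and B1 (B1a and B1b) will be followed until Week 104", and only those at PASI 90 or better continue to Week 208. Protocol 3.1 also removes "Patients who relapse (those who experience a loss of 50% of the maximum improvement in PASI score achieved during the Treatment Epoch"): they have the end-of-study assessments and are then discontinued. Protocol 5.6.6 lists relapse among the mandatory reasons for discontinuation during follow-up.

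**Relapse as non-response.** SAP 2.6.2 and 2.6.3 count relapsers as non-responders in the Week 104 key secondary analysis. No visible text carries that rule past Week 104.

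**The concern.** The denominator after Week 104 is shaped by outcome. One group with incomplete response leaves together at Week 104, and others leave when they relapse. A percentage of those still evaluable therefore describes a different population at Week 116 than at Week 104. From then on it loses failures from the denominator as well as responders from the numerator.

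The stated purpose of the study is prolonged symptom-free periods after early treatment. Weeks 104 to 208 are the Main Study's only data on durability beyond one year after the treatment phase. The plan already recognises the problem at Week 104: it keeps patients without PASI 90 at Week 52 in that analysis to reduce selection bias, and it counts relapse as failure. Both safeguards lapse just as selection becomes stronger. The MCMC difficulty does not explain this for binary endpoints, because NRI fits no model, and NRI is already the planned method for IGA 0/1.

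**Working it through.** The documents give no Week 104 planning rate for IGA 0/1, so PASI 90 is used for illustration.

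**1. Inputs** (Protocol 9.8 and 9.9): 80 per arm; PASI 90 at Week 52 of 70% (A1) and 28% (B1); PASI 90 at Week 104 of 21% and 4%; dropout before Week 104 of 7% and 16%. The plan gives no figure for the period after Week 104, so its key secondary power was reproduced as a check on these rates. Exact enumeration of the 1-sided Fisher test at 0.025, 21% v 4%, 80 per arm, gives 90.0%; the plan states around 89%.

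**2. Counts.**
- A1: responders 0.21 × 80 = 16.8, about 17; dropouts 0.07 × 80 = 5.6, about 6; observed 80 − 6 = 74; Week 52 PASI 90 cohort 0.70 × 80 = 56.
- B1: responders 0.04 × 80 = 3.2, about 3; dropouts 0.16 × 80 = 12.8, about 13; observed 80 − 13 = 67; Week 52 PASI 90 cohort 0.28 × 80 = 22.4, about 22.

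**3. Effect of the planned Week 104 exit alone**, assuming every Week 104 responder was in the Week 52 PASI 90 cohort:

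| Arm | Observed, before exit | Observed, after exit | Share of all randomized |
|---|---|---|---|
| A1 | 17/74 = 23.0% | 17/56 = 30.4% to 17/50 = 34.0% | 17/80 = 21.2%, unchanged |
| B1 | 3/67 = 4.5% | 3/22 = 13.6% | 3/80 = 3.8%, unchanged |

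The A1 range depends on whether the 6 dropouts came from outside the cohort (56 left) or all from within it (56 − 6 = 50). For B1 the second case leaves 22 − 13 = 9, so 3/9 = 33.3%. With dropouts from outside the cohort in both arms, the A1:B1 ratio falls from 23.0/4.5 = 5.1 to 30.4/13.6 = 2.2. The distortion can thus work against secukinumab.

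**4. Sensitivity of step 3.**
- Suppose 25% to 50% of the 80 − 56 = 24 A1 patients below PASI 90 had already left at Week 52 as below PASI 50 (an assumption). The starting rate is then 17/68 = 25.0% to 17/62 = 27.4%, still below 30.4%.
- Suppose 2 to 4 of the 17 A1 responders are in the exiting group (an assumption). The rate after exit is then 13/56 = 23.2% to 15/50 = 30.0%, in some cases slightly below the start. If 2 of the 3 B1 responders exit, the B1 rate is 1/22 = 4.5%, so there is no rise.

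**5. Effect of relapse exit, Weeks 104 to 152, A1 from 17/50.** Two rates per visit are assumed: q, the share of responders losing response, and r, the share of observed non-responders who relapse and leave. Ignoring the one record at the end-of-study visit, the observed rate holds or rises when r × (non-responders / observed) ≥ q. The grid below counts each relapser once as a non-responder at that visit.

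Example, q = 10% and r = 30%:
- Week 116: responders 17 − 1.7 = 15.3; observed 50; rate 30.6%. Then 0.30 × 33 = 9.9 relapsers leave.
- Week 128: responders 13.77; observed 40.1; rate 34.3%.
- Week 140: 37.9%. Week 152: 41.3%.
- Over the same visits responders fall to 17 × 0.9⁴ = 11.15. That is 13.9% of 80, down from 21.2%, and 19.9% of the 56 in the cohort, down from 30.4%.

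Over q = 5% to 20% and r = 10% to 40% (16 settings), the observed rate at Week 152 is within 1 point of 34.0% or above it in 10 settings (33.4% to 59.5%). In the other 6 it falls, but proportionally less than the fixed-denominator rate. With q = 20% and r = 10%, for example, the observed rate keeps 51% of its starting value and the fixed rate 41%. Across all 16 settings the share of 80 falls to between 8.7% and 17.3%.

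**6. The extreme.** SAP 2.14.2 reports 11 patients remaining, arms not stated. If all were Main Study responders, the observed rate would be 100%, against 11/160 = 6.9% of those randomized.

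**The case against.** - **Scope.** The only visible response-rate curve to Week 208 is IGA 0/1. For PASI, SAP 2.5.4 says later data are summarized, and the text on PASI response over time in SAP 2.13 is redacted. This stands: the point covers the IGA curve and the PASI summaries, and no PASI 90 curve after Week 104 can be assumed.
- **Low numbers.** This reason is separate from MCMC and is genuine. It justifies modest displays, but not a denominator that shrinks with outcome.
- **Existing safeguards.** SAP 2.3.1 gives follow-up disposition by Week 52 PASI category, and 2.15.3 gives time to discontinuation. These show who left, but they do not correct the rate.
- **Size of effect.** A reader might infer that the curve must show durable response in both arms and must hide the arm difference. The documents do not support that. Relapsers are assessed once more before leaving, and patients who lose PASI 90 without relapsing stay in follow-up. Six of the 16 settings above show a fall. A rise is possible, not certain.
- **Simple NRI to Week 208.** A reader might infer that everyone no longer observed should count as a failure. That would overcorrect. SAP 2.6.1 counts a patient with PASI 85 at Week 52 and PASI 90 at Week 104 as a responder; that patient would become a non-responder at Week 116 only because follow-up ended. The rule would also fall unevenly: on planning rates 30% of Arm A1 and 72% of Arm B1 are below PASI 90 at Week 52. This stands and shapes the fix.

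**Conclusion.** The concern holds as a presentation problem of moderate weight. After Week 104 the observed rate is conditional on having met PASI 90 at Week 52 and not having relapsed, and the SAP does not label it so. The planned exit alone can add roughly 7 to 11 points in Arm A1 (23.0% to 30.4%-34.0%) and about 9 points in Arm B1 (4.5% to 13.6%). These figures rest on planning rates and on all Week 104 responders coming from the Week 52 PASI 90 cohort; the Arm B1 figure also rests on three responders. The later drift depends on assumed loss and relapse rates that the documents do not give. The visible outputs after Week 104 are descriptive. Nothing here bears on the primary test at Week 52 or the key secondary test at Week 104.

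**What to change.** In SAP 2.5.4, 2.7.1 and 2.13.4, for visits after Week 104:

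1. Present IGA 0/1 and PASI 90 by arm in the Week 52 PASI 90 cohort, the group followed to Week 208 by design, on its fixed Week 52 denominator. Carry relapse and discontinuation for lack of efficacy or AE forward as non-response, and state a rule for other missing values.
2. State the cohort's size as a share of all randomized patients in each arm (on planning rates, 70% and 28%). The cohort is defined after randomization, so the comparison between arms is descriptive.
3. Treat patients stopped by the sponsor's early termination as administratively censored, for example with a Kaplan-Meier curve of time to relapse or loss of response. Do not extend a fixed-denominator proportion past the termination point; SAP 2.14.2 projects the revised last visit at Week 152.
4. Do not count the planned Week 104 exit of Week 52 PASI 50-89 patients as non-response.
5. Keep observed data as a table with n per visit, labelled as conditional on remaining in the study, and do not join it to the imputed curve.

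The cost is a small amount of programming on data already collected, and lower displayed long-term rates.
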